## LIST OF ABBREVIATIONS

ADM	Abductor digiti minimi
ANOVA	Analysis of Variance
BIS/BAS	Behavioral Inhibition System / Behavioral Approach System
CFR	Code of Federal Regulations
CI	Confidence interval
Co-I	Co-Investigator
CRF	Case Report Form
DC	Direct current
DHHS	Department of Health and Human Services
DMV	Department of Motor Vehicles
DSM-5	Diagnostic and Statistical Manual of Mental Disorders (Version 5)
DSMB	Data and Safety Monitoring Board
eCRF	Electronic Case Report Form
EEG	Electroencephalogram
EMG	Electromyography
EOG	Electrooculography
FDA	Food and Drug Administration
GCP	Good Clinical Practice
Hz	Hertz
ICF	Informed Consent Form
ICH	International Conference on Harmonization
IDE	Investigational Device Exemption
IRI	Interpersonal Reactivity Index
M1	Primary motor cortex
NAMI	National Alliance on Mental Illness
NIH	National Institutes of Health
NIMH	National Institute of Mental Health
NRB	Neurosciences Research Building
OCD	Obsessive-Compulsive Disorder
OHRE	Office of Human Research Ethics
OHRP	Office for Human Research Protections
PHI	Protected Health Information
PI	Principal Investigator
PMA	Premarket Approval
SMC	Safety Monitoring Committee
SPI	Serial Peripheral Interface
SOP	Standard Operating Procedure
tACS	Transcranial Alternating Current Stimulation
tDCS	Transcranial Direct Current Stimulation
TEP	TMS-evoked potential
TMS	Transcranial Magnetic Stimulation
UE	Unexpected Event
UNC	University of North Carolina
UNC-CH	University of North Carolina at Chapel Hill

US

United States

**STUDY SUMMARY**

Title	Modulation of motor cortex excitability by transcranial magnetic stimulation and transcranial direct current stimulation
Short Title	TMS
Protocol Number	17-0149
Phase	Pilot
Methodology	Single-site
Study Duration	This study is expected to last 2 month.
Study Center(s)	This is a single-site study performed at The University of North Carolina at Chapel Hill.
Objectives (Purpose)	Purpose of this pilot study is to modulate the motor cortex excitability by transcranial magnetic stimulation and transcranial direct current stimulation. Electromyography will be recorded on right abductor digiti minimi muscle to find the motor threshold and measure motor evoked potentials for each healthy participant. Electroencephalography will be collected on the scalp with a 128-channel net to record TMS-evoked potential.
Number of Subjects	18
Diagnosis and Main Inclusion Criteria	Eligible participants will be healthy individual without any severe illness and mental disorder.
Description of Intervention (Procedures/methods)	Each participant will be seated in a reclining chair and applied non-invasive magnetic and electrical stimulations on the scalp. At baseline, the participant's resting motor threshold (RMT) will be estimated by adjusting the intensity of TMS applied on the left motor cortex to achieve an MEP of about 50uV with 10 TMS pulses at a rate of 0.25Hz. Then a 3-condition, 3-session, 6-sequence randomized crossover experiment will be used to characterize and compare three versions of tDCS stimulation: anode, cathode, sham. Before and after a 10-min tDCS condition is applied, TMS pulses at 120% of RMT intensity will be applied for 5 minutes and TEP and MEP amplitude will be measured.
Related IRB Applications	n/a

**1.4 FUNDING SOURCES**

Please list below the funding sources for this project:

Sponsor Name	UNC Ramses Number	Sponsor Type	Prime Sponsor Name	Prime Sponsor Type	Sponsor/Grant Number
Foundation of Hope for Research and Treatment of Mental Illness	17-2460	Foundation/Non-Profit	Foundation of Hope for Research and Treatment of Mental Illness	Foundation/Non-Profit	Not applicable

**External Funding:** This project is externally funded but UNC-CH is not the direct recipient of federal funds.

**UNC-CH Funding:** This project is not funded through UNC-CH.

**Classified:** This project is not classified.

## 2 INTRODUCTION

This document is a protocol for a human research study. This study is to be conducted according to U.S. and international standards of Good Clinical Practice (FDA Title 21 Part 312 and International Conference on Harmonization guidelines), applicable government regulations and Institutional research policies and procedures.

### 2.1 BACKGROUND

Neuronal activity is coded by the frequency of spike firing, which in turn is controlled by the level of the neuronal membrane potential. While more positive potentials lead to increased discharge rates, more negative potentials are associated with reduced firing rates. Transcranial direct current stimulation (tDCS) modulates these processes selectively, depending on the current polarity, duration or strength, and is capable of inducing after-effect excitability changes in the human motor cortex (Nitsche and Paulus, 2000; Baudewig et al., 2001). These features favour the evolution of the tDCS technique as a promising tool in neuroplasticity research as well as a therapeutic instrument in neurological disorders associated with hyper- or hypoexcitable cortex. Previous studies have shown that cerebral excitability was diminished by cathodal stimulation (hyperpolarization) and anodal stimulation leads to an increase in excitability (depolarization) in animal (Bindman et al., 1962; Purpura and McMurtry, 1965). In humans, one study first demonstrated it in invasive epilepsy diagnostics by applying intracranial currents of sufficient strength at intensities of up to 1.5 mA (Dymond et al., 1975). In a non-invasive manner, weak tDCS can alert the cortical excitability using surface electrodes on the scalp (Nitsche and Paulus, 2001, 2000). tDCS differs qualitatively from other brain stimulation techniques because static fields do not yield the rapid depolarization required to produce action potentials in neural membranes (Nitsche et al., 2008). However, tDCS might be considered a neuromodulatory intervention.

Transcranial magnetic stimulation (TMS) is one method used to deliver electrical stimuli through the scalp in humans. In general, single-pulse TMS (including paired-pulse TMS) is used to explore brain functioning, whereas repetitive TMS (rTMS) is used to induce changes in brain activity that can last beyond the stimulation period. Non-invasive TMS of the motor cortex leads to a twitch in the target muscle evoking motor-evoked potential (MEP) on electromyography (EMG). The MEP is usually used to assess the corticospinal tract excitability. On the basis of the computational model (Tofts, 1990), TMS preferentially activates neurons oriented horizontally in a plane that is parallel to both the coil and the brain surface. TMS applied over the motor cortex induces descending volleys in the pyramidal tract projecting on spinal motoneurons, also termed corticospinal tracts. Motoneuron activation in response to corticospinal volleys induced by TMS evokes MEP on EMG recorded by using surface electrodes applied over the muscle belly. In practice, the peak-to-peak amplitude of the MEP and the motor threshold, defined by the minimum TMS intensity required to evoke MEP of at least 50  $\mu$ V in about 50% of 5 to 10 consecutive trials (Borojerdj et al., 2001), are both parameters used to estimate the excitability of corticospinal pathways. In addition, combining TMS with electroencephalography (EEG) can capture cortical excitability beyond corticospinal excitability since EEG mainly captures neural activity of the cortical neurons (Farzan et al., 2016). The concurrent combination of TMS with EEG can be a powerful technology for characterizing and modulating brain networks by obtained TMS-evoked potentials (TEPs).

## 2.2 DOSE RATIONALE

In this study, our primary purpose is to investigate the level at which polarizing currents affect the excitability of the corticospinal system including sham condition. Although it may seem most likely that polarizing currents affect excitability of cortical mechanisms, it is possible that application of the current alters the tonic level of background activity in corticospinal systems and that this produces secondary changes in the excitability of spinal mechanisms that outlast the duration of the stimulus current.

Specifically, we propose an experimental design to modulate motor excitability by different polarity (anode and cathode) and sham of tDCS in human brains. As previous studies showed, tDCS induces persisting excitability changes in the human motor cortex and these plastic excitability changes are selectively controlled by the polarity of tDCS. To reveal the underlying mechanisms of direct current-induced neuroplasticity, we will apply tDCS with 3 different conditions (anode, cathode and sham) and TMS on the motor cortex. Induced cortical- and corticospinal-excitability changes will be assessed by TEPs and MEPs based on individual motor threshold. To reduce a spatial mismatch for targeting primary motor cortex (Diekhoff et al., 2011), in addition, we will collect subjects' individual structural MRI.

## 2.3 STUDY AIMS/HYPOTHESES

---

### 2.3.1 SPECIFIC AIMS

Aim 1. For each tDCS condition, estimate mean changes in TEP and MEP amplitudes induced by tDCS stimulation.

Aim 2. Compare the three tDCS conditions (anode, cathode, sham) in terms of the mean changes in TEP and MEP amplitude.

Aim 3. Obtain statistical estimates of variance components needed for the planning of a future study.

---

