### 2.3.2 RESEARCH HYPOTHESES

We hypothesize that anodal and cathodal tDCS stimulation increases and decreases TEP and MEP amplitudes compare to sham tDCS condition, respectively. We further hypothesize that TEP and MEP amplitudes are positively correlated.

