### 11.1 STATISTICAL ANALYSIS STRATEGIES

To help ensure reproducible results, these a priori plans specify the planned analyses for each specific aim along with guidelines for sensitivity analyses performed to assess the robustness of the major results to reasonable perturbations of the assumptions, choices, and methods used. The plans also include 1) secondary analyses as an aid for understanding and interpreting the main analysis results, 2) a role for exploratory analyses for hypothesis generation, and (3) necessary descriptive graphical and tabular methods used to visualize the data, examine relationships among variables, and characterize the participants.

Immediately before and after a 10-min tDCS treatment is applied, TMS pulses at 120% of RMT intensity will be applied for 10 minutes at a frequency of 0.25Hz. For each of those 75 TMS pulses, the MEP amplitude will be measured by EMG in the ADM muscle. Thus, we will have 75 MEP amplitudes before and after each of the 3 tDCS conditions is applied. (In total, each subject contributes 450 MEP amplitudes.) For each set of 75 amplitudes, we will compute the average amplitude. The change in average amplitude ( $\Delta A_{ij}$ ) will be computed as the post-tDCS average minus the pre-tDCS average:  $\Delta A_{ij^*} = A_{ij^*}(post) - A_{ij^*}(pre)$  for the  $i^{th}$  subject and the  $j^{th}$  tDCS condition. The primary analysis will focus on these changes in average amplitude and will rely on a linear mixed-effects model which assumes a compound-symmetry covariance matrix; in other words, a repeated-measures ANOVA model. The dependent variable will be the change in average amplitude ( $\Delta A_{ij^*}$ ) and the explanatory variables will be tDCS treatment condition, treatment period, sequence group ( $v$ ), and indicator variables representing carryover effects ( $\lambda$ ).

Entry is the expected value of $\Delta A_{ij^*}$ in the target population	Period 1	Period 2	Period 3
Sequence ACS	$\mu_A + v_1 + p_1$	$\mu_C + v_1 + p_2 + \lambda_A$	$\mu_S + v_1 + p_3 + \lambda_C$
Sequence ASC	$\mu_A + v_2 + p_1$	$\mu_S + v_2 + p_2 + \lambda_A$	$\mu_C + v_2 + p_3 + \lambda_S$
Sequence CAS	$\mu_C + v_3 + p_1$	$\mu_A + v_3 + p_2 + \lambda_C$	$\mu_S + v_3 + p_3 + \lambda_A$
Sequence CSA	$\mu_C + v_4 + p_1$	$\mu_S + v_4 + p_2 + \lambda_C$	$\mu_A + v_4 + p_3 + \lambda_S$
Sequence SAC	$\mu_S + v_5 + p_1$	$\mu_A + v_5 + p_2 + \lambda_S$	$\mu_C + v_5 + p_3 + \lambda_A$

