Sequence SCA	$\mu_S + v_6 + p_1$	$\mu_C + v_6 + p_2 + \lambda_S$	$\mu_A + v_6 + p_3 + \lambda_C$

Note: We define  $v_6 = (-1) * (v_1 + v_2 + v_3 + v_4 + v_5)$  and  $p_3 = (-1) * (p_1 + p_2)$

The fitted model will be used to tabulate statistical estimates (all with 95% confidence intervals) of the parameters of interest: variance components, intra-class correlations, direct effects of tDCS ( $\mu$ ), period effects ( $p$ ), sequence-group effects ( $v$ ), and first-order carryover effects of tDCS ( $\lambda$ ). We will assume that there are no differential second-order carryover effects. The fitted model will also be used to test the main hypothesis,  $H_o: "(\mu_A - \mu_S) = 0 = (\mu_A - \mu_S)"$ , using an F-test of size  $\alpha = 0.05$ . If (and only if) this null hypothesis is rejected, then (and only then) we will test the two component sub-hypotheses using F-tests of size  $\alpha=0.05$ :  $H_{oA} (\mu_A - \mu_S)=0"$ ,  $H_{oC} "(\mu_C - \mu_S) = 0"$ .

We will also perform an equivalence test in which equivalence is defined as a difference of less than  $0.1mV$  (i.e., tolerance  $T = 0.1mV$ ). The null hypothesis that the anode and cathode stimulation are not equivalent is  $H_0 = "|\mu_A - \mu_C| > T = 0.1mV"$ . The null hypothesis will be rejected if the 95% confidence interval for  $(\mu_A - \mu_C)$  lies entirely within the interval  $[-T, T]$ .

All hypothesis tests that are observed to be NOT statistically significant will be reported as being inconclusive. Hypothesis tests that are not statistically significant are entirely inconclusive and no conclusions can be drawn from those tests. Every statistical test procedure is (by definition) incapable of establishing that the null hypothesis is true. The word "inconclusive" will be used when reporting a test that was not statistically significant. To avoid over-reliance on p-values, the focus of the analyses will be on point-estimates and interval-estimates of the magnitudes of the population parameters of interest (e.g, effects, correlations, variance components.)

In secondary analyses, time-specific changes in amplitude will be computed as  $\Delta A_{ijT} = A_{ijT}(post) - A_{ijT}(pre)$  for  $T = 1, 2, 3, \dots, 75$ . Graphical descriptive statistical methods will be used to visualize and summarize the temporal trajectories of MEP amplitudes.

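### Aim 1 and the tabulated direct effects credit uncontrolled pre-to-post changes, sham included, to tDCS; the differences from sham should be named as the effects and tabulated with 95% CIs

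*Combined protocol and SAP*

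**What the plan says.** Section 2.3.1 states Aim 1 as "For each tDCS condition, estimate mean changes in TEP and MEP amplitudes induced by tDCS stimulation". Aim 2 is "Compare the three tDCS conditions (anode, cathode, sham) in terms of the mean changes in TEP and MEP amplitude", so sham counts as one of the tDCS conditions to which Aim 1 applies. The hypothesis in Section 2.3.2, by contrast, is relative to sham: "anodal and cathodal tDCS stimulation increases and decreases TEP and MEP amplitudes compare to sham tDCS condition, respectively".

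In Section 11.1 the outcome for each participant and condition "will be computed as the post-tDCS average minus the pre-tDCS average". The table of expected values gives each cell the μ of its own condition plus sequence, period and carryover terms. Sequence and period terms are set to sum to zero; no constraint is given for the three carryover terms. Estimates with 95% confidence intervals are then promised "of the parameters of interest: variance components, intra-class correlations, direct effects of tDCS", with μ as the symbol for the last of these, followed by period, sequence-group and carryover effects.

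Differences from sham appear by name only in the F-tests: a global test, then one test each for anode and cathode against sham. (The global null as printed repeats the anode-sham difference.) The one difference with a named confidence interval is anode minus cathode, for the equivalence test.

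**The concern.** A change from before to after stimulation contains whatever differs between the two TMS blocks: a tDCS effect if there is one, but also shifts in arousal, muscle state, or coil and electrode set-up. Only the comparison with sham separates these. Aim 1 and the μ table nevertheless put a causal label on the uncontrolled change, and do so even for sham, which Section 4 describes as the control.

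The plan puts estimates ahead of p-values and exists to inform a future study. If Aim 1 is reported as worded, a change that is only drift can be written up as caused by anodal, cathodal or even sham stimulation, while the quantity that answers the stated hypothesis is left to general wording.

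**Working it through.** The plan gives no SD, drift size or effect size, so it has no figure of its own to reproduce here. The precision statement in the sample-size section concerns a proportion and does not bear on this point.

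**1. What μ contains.** Suppose there is no tDCS effect and every session drifts by d. Every cell mean in the Section 11.1 table then equals d. The period terms cannot absorb it, because they sum to zero, and neither can the sequence terms. With carryover omitted, constrained to sum to zero, or set to zero for sham, the fit gives μ_A = μ_C = μ_S = d. For an assumed d = 0.1 mV, all three μ estimates are 0.1 mV, while μ_A − μ_S = 0 and μ_C − μ_S = 0.

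**2. Whether μ can be estimated as written.** The mean parameters are 3 (μ) + 5 (sequence) + 2 (period) + 3 (carryover) = 13. The design matrix for 6 sequences × 3 periods has rank 12. The redundancy can be shown directly. For any c, add c to each λ, add 2c/3 to p₁, subtract c/3 from p₂ and p₃, and subtract 2c/3 from each μ.

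- Period 1: −2c/3 + 2c/3 = 0.
- Periods 2 and 3: −2c/3 − c/3 + c = 0.
- Period terms still sum to zero: 2c/3 − c/3 − c/3 = 0.

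No expected value changes, yet every μ moves by the same amount. No single μ is therefore estimable, while μ_A − μ_S, μ_C − μ_S and μ_A − μ_C are. For example, the minimum-norm solution for the 0.1 mV drift has each λ = 0.0409, so each μ = 0.1 − (2/3)(0.0409) = 0.0727 mV; the contrasts remain 0.

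**3. How often drift would look like an effect.** These are assumptions, for illustration only: no tDCS effect, n = 18, a one-sample 95% t interval for one condition, and drift in SDs of the change score. The chance that the interval excludes zero comes from the noncentral t with 17 df and noncentrality (drift/SD) × √18, where √18 = 4.243.

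| Drift/SD | Noncentrality | Interval excludes 0 |
|---|---|---|
| 0.25 | 1.061 | 17% |
| 0.50 | 2.121 | 52% |
| 0.75 | 3.182 | 85% |
| 1.00 | 4.243 | 98% |

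Standard errors from the crossover model (compound symmetry; correlation 0 or 0.5; carryover constrained to sum to zero, or omitted) give similar values: about 16–18%, 47–54% and 96–98% at 0.25, 0.5 and 1.0 SD.

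**4. Precision of the contrasts.** With subject, period, treatment and first-order carryover effects, residual df = 54 − 18 − 2 − 2 − 2 = 30. The variance of a treatment contrast is 0.1389σ², with σ the within-subject SD. The 95% half-width is 2.042 × √0.1389 × σ = 0.761σ. This is unaffected by common drift.

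**The case against.** The strongest reply is that this is mostly wording. Much of it stands.

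- *A reader might infer that the sham differences get F-tests and nothing else, or that they are absent from the planned outputs.* The documents do not support that. Section 11.1 says that "the focus of the analyses will be on point-estimates and interval-estimates of the magnitudes of the population parameters of interest", with effects among its examples, and its paragraph on Aim 3 promises intervals for the estimates needed to plan a future study. Section 11.2 makes clear that these go beyond variance components. The sham differences are not named in either place, but they can be read in.
- *A reader might infer that intervals for the differences could not be recovered from the planned table.* That does not follow. Subtracting two μ estimates gives the contrast, and the variance components are tabulated too. With complete data in this balanced design, the within-subject SD and the 0.761 multiplier give the half-width.
- *The word direct* is standard crossover language for the effect of the current period's condition as opposed to carryover. It does not by itself claim freedom from drift.
- *A reader might infer that drift undermines the main result.* It does not. Aim 2, the hypotheses and the gated tests compare conditions, and no test of μ = 0 is planned. Showing μ_S beside the others would also reveal a common drift to an alert reader.

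None of this removes the attribution in Aim 1, which has no sham comparison in it, or the listing of three separate μ values that the written model cannot estimate.

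**Conclusion.** The point holds as one of labelling and reporting. Aim 1 and the μ table attribute uncontrolled within-session changes, sham's included, to tDCS. All of a drift common to the conditions enters each μ, and none enters the contrasts. Without a carryover constraint the separate μ values are not identified, and choosing a constraint does not remove the drift. The differences from sham, which answer the stated hypothesis, are not explicitly listed for tabulation.

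The 17% to 98% range rests on assumed drifts of 0.25 to 1.0 SD and a simple one-sample interval. It shows sensitivity and is not a forecast for this trial. The protection given by the contrasts assumes that the drift is the same in all conditions. The plan should be changed, but its main tests are not invalidated on this ground.

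**What to change.** In Section 2.3.1, reword Aim 1 to estimate the *mean change from before to after stimulation in each condition*, without attributing it to stimulation.

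In Section 11.1, define the tDCS effects as μ_A − μ_S and μ_C − μ_S, and list these together with μ_A − μ_C for tabulation with 95% confidence intervals from the fitted model. State the carryover constraint. Report μ_A, μ_C and μ_S under that constraint only as descriptive within-session changes that include drift, and do not label μ_S a tDCS effect.

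The cost is a few wording changes, one stated constraint and three contrast statements from a model already planned. No new data or design change is needed.

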### 2.3.2 RESEARCH HYPOTHESES

We hypothesize that anodal and cathodal tDCS stimulation increases and decreases TEP and MEP amplitudes compare to sham tDCS condition, respectively. We further hypothesize that TEP and MEP amplitudes are positively correlated.

### 3 SUBJECT SELECTION AND WITHDRAWAL

A total of 18 participants will be recruited for this study and all data will be collected at UNC-CH. No specific plans have been made to enroll participants from vulnerable populations.

#### 3.1 INCLUSION CRITERIA

In order to be eligible to participate in this study, a participant must meet all of the following criteria:

- Males
- Between the ages of 18 and 35
- Right handed
- Capacity to understand all relevant risks and potential benefits of the study (informed consent)
- Willing to comply with all study procedures and be available for the duration of the study
- Speak and understand English

#### 3.2 EXCLUSION CRITERIA

A potential participant who meets any of the following criteria will be excluded from participation in the study:

- Prior concussion
- Diagnosis of eating disorder (current or within the past 6 months)
- Diagnosis of OCD (lifetime)
- ADHD (currently under treatment)
- Neurological disorders and conditions, including, but not limited to:
  - History of epilepsy
  - Seizures (except childhood febrile seizures and ECT-induced seizures)
  - Dementia
  - History of stroke
  - Parkinson's disease
  - Multiple sclerosis
  - Cerebral aneurysm
  - Brain tumors
- Medical or neurological illness or treatment for a medical disorder that could interfere with study participation (e.g., unstable cardiac disease, HIV/AIDS, malignancy, liver or renal impairment)
- Prior brain surgery
- Any brain devices/implants, including cochlear implants and aneurysm clips
- Traumatic brain injury
- (For females) Pregnancy or breast feeding
- Anything that, in the opinion of the investigator, would place the participant at increased risk or preclude the participant's full compliance with or completion of the study

**Justifications for any exclusions based on race, gender, or ethnicity:** Non-English speaking individuals are excluded because the ability to accurately and completely communicate study information, answer questions about the study, and obtain consent are necessary.

Previous studies (Becker et al., 1982; Creutzfeldt et al., 1976; Solis-ortiz et al., 1994) demonstrated that there are significant changes in EEG activity with changed hormone levels and spontaneous menstrual cycle. One study revealed that luteal and follicular women showed higher and lower alpha oscillations in resting-state EEG compared to healthy men (Brötzner et al., 2014), respectively. In addition to EEG activity, one study found that modulating cortical excitability by TMS is affected by menstrual cycle. They applied TMS pulses to 13 healthy women (luteal and follicular) and found significant changes ( $p < 0.01$ ) in cortical excitability. This study provides the direct evidence of changes in the excitability of a cortical network with the menstrual cycle.

In theory, one could measure female subjects twice during their early follicular phase ( $\pm 28$  days). However, practically this approach is very difficult to conduct and has some limitations. First, one would need female subjects that have an exact menstrual cycle of 28 days in order to measure at the same weekday and that the time interval. Such a population is very difficult to find and would need at least a 6 month evaluation period of females that have a very stable menstrual cycle. Second, according to literature, the observed variations in EEG activity might reflect the fluctuating actions of the female hormones estrogen and progesterone (Bäckström, 1976). Thus, we would need to control for plasma female hormone levels to assure that those levels were similar for the three tDCS conditions. Thus, because we aim at investigating modulation of cortical excitability with EEG, we need a study population that shows stable EEG activity and excitability.

**Justification for excluding women or women who become pregnant:** Pregnant participants will be excluded despite the fact that theoretical risk to mother or fetus is exceedingly small, since no safety data for pregnancy is known to exist for TMS/tDCS studies. We will verify pregnancy status via a urine pregnancy test for all female participants.

